# 1.1. PROTOCOL SYNOPSIS

Sponsor	Vanderbilt-Ingram Cancer Center									
Protocol Title	BRE 17107: A Phase Ib/II Trial of Atezolizumab (an anti-PD-L1 monoclonal antibody) with Cobimetinib (a MEK1/2 inhibitor) or Idasanutlin (an MDM2 antagonist) in Metastatic ER+ Breast Cancer									
Protocol Number	BRE 17107									
Phase of Development	Phase Ib/II									
Investigational Product and Mechanism	
 
Cobimetinib - MEK inhibitor
 
Idasanutlin - MDM2 antagonist
 
Atezolizumab - PD-L1 inhibitor
 
									
Treatment Schedule Dose/Route	
 
Cobimetinib 60 mg PO Days 1 – 21, every 28 days
 
Idasanutlin (final dose to be determined by the phase Ib portion of the study) PO Days 1 – 5, every 28 days
 
Atezolizumab 840 mg IV on Days 1 and 15, every 28 days
 
									
Objectives	
 
Phase Ib portion: determine the safety and tolerability of ATEZO and IDASA in patients with ER+ mBC
 
Phase II portion: determine the anti-tumor effect and adverse effects profile of ATEZ with COBI or IDASA in patients with ER+ mBC
 
									
Endpoints	
 
Primary Endpoint:
 
Phase Ib: Dose Limiting Toxicity (DLT), Maximum Tolerated Dose (MTD) and Recommended Phase II Dose (RP2D) determination for the ATEZO and IDASA combination
 
Phase II: Progression Free Survival (PFS) for each treatment arm
 
Secondary Endpoints:
 
Clinical Benefit Rate (CBR; percentage of patients without disease progression at 6 months) for each treatment arm
 
Immune-related Response Criteria (irRC),
 
Duration of Response (DOR)
 
Overall Response Rate (ORR; by RECIST 1.1 – for patients with measurable disease),
 
Percentage of patients alive at 12 months (% OS)
 
Adverse Event profile for each treatment arm
 
									
Trial Design	Other: Exploratory Endpoints  This is an open-label, multicenter, two-arm phase Ib/II clinical trial that will evaluate the anti-tumor effect of atezolizumab (ATEZ; an anti- PD-L1 mAb) in combination with cobimetinib (COBI; a MEK inhibitor) in patients with TP53-mutated ER+ mBC, or idasanutlin (IDASA; an MDM2 antagonist) in patients with TP53-wt ER+ mBC.									

NI I	DI II : : (0 : (40 !/ :
Number of Patients	Phase Ib: minimum of 9, maximum of 18 patients     Phase II: minimum of 23, maximum of 66 patients

Patient Selection	
 
Inclusion Criteria
 
1. Signed and dated written informed consent.
 
2. Subjects ≥ 18 years of age.
 
3. Eastern Cooperative Oncology Group (ECOG) performance status 0 or 1.
 
4. Clinical stage IV invasive mammary carcinoma or unresectable locoregional recurrence of invasive mammary carcinoma that is: 
 
ER/PR-positive (> 1% cells) by IHC and HER2 negative (by IHC or FISH)
 
Previously exposed to an aromatase inhibitor (AI) or a selective estrogen-receptor modulator/ downregulator (SERM; SERD) + a CDK4/6 inhibitor
 
Appropriate candidates for chemotherapy
 
Amenable to biopsy at the time of study entry
 
 
 
5. Adequate organ function including: 
 
Absolute neutrophil count (ANC) ≥ 1.5 × 10^9/L
 
Platelets ≥ 100 × 10^9/L
 
Platelets ≥ 100 × 10^9/L
 
Hemoglobin ≥ 9/g/dL (may have been transfused)
 
Total serum bilirubin ≤ 1.5 times upper limit of normal (ULN)
 
Aspartate aminotransferase (AST/SGOT) and alanine aminotransferase (ALT/SGPT) ≤ 2.5 × ULN (or ≤ 5 × ULN if liver metastases are present)
 
Serum creatinine ≤ 1.5 x ULN or estimated creatinine clearance ≥ 50 mL/min as calculated using the Cockcroft-Gault (CG) equation
 
Thyroid Stimulating Hormone (TSH) ≤ 1 x ULN
 
Amylase ≤ 1 x ULN
 
Lipase ≤ 1 x ULN
 
CPK ≤ 1.5 x ULN
 
 
 

- LVEF (echo) ≥ LLN (Cobi arm only)
- 6. Female patients of childbearing potential must agree to use at least two methods of acceptable contraception from 15 days prior to first trial treatment administration until at least 5 months after study participant's final dose of study drugs. See appendix C for details.

**Note:** Females of childbearing potential are defined as those who are not surgically sterile or post-menopausal (i.e. patient has not had a bilateral tubal ligation, a bilateral oophorectomy, or a complete hysterectomy; or has not been amenorrheic for 12 months without an alternative medical cause). Post-menopausal status in females under 55 years of age should be confirmed with a serum follicle-stimulating hormone (FSH) level within laboratory reference range for postmenopausal women.

- 7. Patients unable to read/write in English are eligible to participate in the overall study but will not participate in the Patient-Reported Outcome questionnaires throughout the trial
- 8. Re-enrollment of a subject that has discontinued the study as a pretreatment screen failure (i.e. a consented patient who did not receive study drugs) is permitted. If re-enrolled, the subject must be reconsented. Only the screening procedures performed outside of protocol-specified timing must be repeated.

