### 5. REGISTRATION PROCEDURES

### 5.1. Guidelines for VICC and Participating Institutions

Prior to registration, a copy of the IRB approval at the site will be requested and kept on file at the Vanderbilt-Ingram Cancer Center (VICC) Coordinating Center. Eligible participants will be entered on study centrally at the VICC Coordinating Center. All sites should email the Coordinating Center at [contact] to verify treatment availability prior to enrollment.

All patients MUST be registered with the VICC prior to the start of protocol treatment. Registration can only be conducted during the business hours of 8AM - 5PM Monday through Friday.

- 1) All sites should email the VICC CTSR Coordinating Center at [contact] to notify of upcoming registration and slot availability.
- 2) If a subject ID number is required prior to patient enrollment (i.e. screening tissue to be collected), the site must submit the following documents with their email notification to the Coordinating Center:
  - Copy of the patient's signed and dated Informed Consent including documentation of the consent process.
  - HIPAA authorization form (if separate from the main consent form)
  - VICC Patient Enrollment Form

The Coordinating Center will then provide a subject ID number via email.

- 3) After following your site's eligibility verification procedures, email the following documents to the VICC Coordinating Center for sponsor eligibility review and patient enrollment ([contact]):
  - Copy of the patient's signed and dated Informed Consent, including documentation of the consent process.
  - HIPAA authorization form (if separate from the main consent form)
  - VICC Patient Enrollment Form
  - Copies of laboratory, imaging and pathology reports
  - Tissue Block Registration Form (see the **Lab Manual**)
  - Completed Eligibility Checklist, including all supporting source documents. To be eligible for registration to the study, the participant must meet each inclusion and exclusion criterion listed in the eligibility checklist.

Note: VICC Coordinating Center requests 24-48 hours to review all documents and confirm eligibility. Same day treatment registrations will only be accepted with prior notice and discussion with the Coordinating Center. Please email the Coordinating Center if enrollment is needed sooner.

Once registration/enrollment confirmation from Coordinating Center is received, proceed with protocol procedures.

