Please contact the assigned Project Manager or Regulatory Coordinator with any questions regarding this process. You can also reach out to your assigned CRA once the study is activated.

The VICC Coordinating Center will assign sequence numbers to all patients in screening. Only patients deemed eligible will be registered to investigational treatment. Sequence numbers will not be re-used if a patient screen fails unless the same patient re-screens at a later point. Following registration, eligible participants should begin study treatment consistent with the protocol no later than 3 weeks after registration/enrollment by the VICC Coordinating Center. If a participant does not receive protocol therapy following registration within the allowed time period (2 weeks), the participant's registration on the study may be canceled. The assigned CRA should be notified of cancellations as soon as possible.

Issues that would cause treatment delays should be discussed with the Protocol Chair. If a participant does not receive protocol therapy following enrollment within allowed time period (2 weeks), the participant will become ineligible and will be removed from the study. Such patients will have to undergo re-screening in order to participate in the study.

As is generally accepted, standard of care procedures performed prior to consent, but within the protocol defined screening window for each assessment, can be used for study purposes. All research-only procedures must be performed after the consent date.

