# 6. STUDY CALENDAR

		Week/Cycle											
Parameter	Pre- Treatment 	C1 D1	C1D8	C1 D15	C1 D1,8, 15, 22 	C2 D1	C2 D15	C3D1	D1 Every Cycle	D15 Every Cycle	Day 1 of Every Odd Cycle except Cycle 1	Every 12 weeks from C2D1 onwards	End of Treatment 
Demographics	х												
	,				CLIN	IICAL EV	ALUATION	IS:					,
History and Physical	x				x		X12		х				х
Height	х												
Vital signs and Weight 	х				х		X12		х	х			х
Performance status	х				х		X12		х				х
Ophthalmologic evaluation 	х					х						х	
				L	ABORATOR'	Y/RADIOI	LOGIC EV	LUATION	IS:	"			
Hematology (CBC/diff, plt)	х				Х		X12		х				
Comprehensive Metabolic Panel 	х			х	Х		X12		х				
Pregnancy Test 	х										х		
Phosphorus		х							х				
Uric Acid		х							х				
СРК	х								х				
Amylase/ Lipase	х										х		
Echocardiogram 	х					х						х	
Thyroid Stimulating Hormone (TSH)	х								х				
HCV antibody and HBV surface antigen	х												
TP53 status 	х												
Tumor Assessments through Imaging Studies 	х										х		

		Week/Cycle											
Parameter	Pre- Treatment 	C1 D1	C1D8	C1 D15	C1 D1,8, 15, 22 	C2 D1	C2 D15	C3D1	D1 Every Cycle	D15 Every Cycle	Day 1 of Every Odd Cycle except Cycle 1	Every 12 weeks from C2D1 onwards	End of Treatment 
			•		TREAT	MENT A	OMINISTRA	TION		•		•	
Atezolizumab			IV once every 2 weeks starting on Cycle 1 Day 15										
Cobimetinib ( TP53 -mut arm)			PO once daily from Day 1 – 21 starting on Cycle 1 Day 1										
ldasanutlin ( TP53- wt arm)		PO once daily from Day 1 – 5 starting on Cycle 1 Day 1											
					COF	RRELATI	/E STUDIE	S:					
Tumor Biopsy 	х			х									
Blood collection 		х		х				х					х
ADDITIONAL INFORMATION:						·							
Concomitant Medications Review		х							х	х			х
Adverse Events Assessment							X (AE will	be assess	sed through	hout the st	udy)		

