#### Note:

- ☐ Additional tests may be performed at the discretion of the treating investigator as clinically indicated.
- The sample collection schedules outlined above are based on an ideal subject. The sample schedule should be followed as closely as is realistically possible; however, the schedule may be modified (± 4 business days) due to problems such as scheduling delays or conflicts (e.g., clinic closure, poor weather conditions, vacations, etc.).
- □ Items highlighted in grey are performed for research purposes (not standard of care)
  - 1. Within 4 weeks prior to starting treatment, unless otherwise noted.
  - 2. Serum chemistry includes measurement of sodium, potassium, chloride, bicarbonate, BUN, creatinine, glucose, total bilirubin, calcium, total protein, albumin, AST, ALT, and alkaline phosphatase.
  - 3. On days of Atezolizumab treatment, Pre-Dose vitals should respectively be recorded ≤ 60 minutes prior to the start of the Atezolizumab infusion. Post-Dose vitals should be recorded during and after infusion only if clinically indicated.
  - 4. Baseline evaluation of disease status by CT or MRI within 28 days prior to first dose of study drugs. Baseline and subsequent scans to include imaging of the chest, abdomen and pelvis. The first scheduled re-scan should be performed and evaluated 7 to 8 weeks after Cycle 1, Day 1 treatment, with subsequent scheduled scans intended every ~ 8 thereafter. Scanning on the same day as dosing is discouraged but allowed, provided scan results receive appropriate evaluation prior to study

- treatment. Additional disease evaluations or increased scan frequency may be performed according to the medical judgment of the patient's study physician.
- 5. Fresh biopsy in consenting patients (including those with pre-existing archival tissue) with primary or metastatic lesion judged amenable to medically safe excisional, incisional or core needle biopsy.
- 6. A 1-month follow-up clinic visit is intended 28 days (±7 days) after the preceding End-of-Treatment visit. Documented attempt(s) should be made for patient return to the study clinic. It will not be considered a protocol deviation if the patient is physically unable to return for the follow-up visit; such circumstance should be recorded in the study documents, and as much of the follow-up information as possible should be obtained via feasible patient contact and from local and outside facilities.

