- 7. If a patient discontinues the study for reason other than progressive disease confirmed by CT or MRI (e.g. adverse event), then CT or MRI scans of the chest, abdomen and pelvis should be continued every 8-9 weeks until disease progression is confirmed by imaging.
- 8. For tissue collection, refer to Lab Manual for details of collection, processing and shipping.
- 9. For peripheral blood, refer to **Lab Manual** for details of collection, processing and shipping
- 10. Please note on Section 10 and Lab Manual that both FFPE and fresh tissue should be obtained.
- 11. Complete ophthalmologic exams will be performed prior to treatment initiation, cycle 2 day 1 (± 1 week), and every 12 weeks from then on (± 2 weeks) on patients in the cobimetinib arm only. Complete ophthalmologic examination will be performed and interpreted by a qualified ophthalmologist, including visual acuity testing, intraocular pressure measurements by tonometry, slit-lamp ophthalmoscopy, indirect ophthalmoscopy, and spectral domain optical coherence tomography. Ophthalmologic examination may be performed up to 42 days prior to starting study treatment.
- 12. For patients on the phase Ib portion of the study only (idasanutlin arm only)
- 13. Only for women of childbearing potential
- 14. Evaluation of LVEF by Echocardiogram should be performed prior to treatment initiation, cycle 2 day 1 (± 1 week), and every 12 weeks from then on (± 2 weeks) on patients in the cobimetinib arm only. The treatment discontinuation visit evaluation of LVEF does not need to be performed at the treatment discontinuation visit if an evaluation has been performed within the last 12 weeks and there are no clinically significant findings and/or changes from baseline. All patients restarting treatment with a dose reduction of cobimetinib because of a decrease in LVEF should have LVEF measurements taken after approximately 2 weeks, 4 weeks, 10 weeks, and 16 weeks, and then resume monitoring of LVEF every three treatment cycles. Any patient who develops clinical signs or symptoms suspicious of cardiac failure should undergo an LVEF assessment.
- 15. *TP53* mutation status may be known based on previously checked NGS or cfDNA commercially available assays. If not known, an archival FFPB should be sent to the Sponsor (see Section 10 and **Lab Manual**) for *TP53* mutation status determination.

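### The only scheduled pregnancy test before dosing can be taken up to 13 days before contraception has to start, and the next is not until Cycle 3 Day 1

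*Combined protocol and SAP*

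**What the plan says.** **Contraception.** Inclusion criterion 6 in the synopsis asks for "at least two methods of acceptable contraception from 15 days prior to first trial treatment administration". Section 4.1 and Appendix B use the same start, 15 days before the first dose.

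**Testing.** In the Study Calendar (section 6), the row "Pregnancy Test" is marked in two columns: Pre-Treatment, and "Day 1 of Every Odd Cycle except Cycle 1". Note 1 sets the window for the Pre-Treatment column: "Within 4 weeks prior to starting treatment, unless otherwise noted". The test's own note, 13, reads "Only for women of childbearing potential". It says who is tested and gives no timing.

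**Registration and start.** Under section 5.1, "the participant must meet each inclusion and exclusion criterion listed in the eligibility checklist", and the "VICC Coordinating Center requests 24-48 hours to review all documents and confirm eligibility". Two sentences in 5.1, and section 7.2, allow 2 weeks from registration or authorization to the first dose; one sentence in 5.1 allows 3 weeks. Exclusion 17 bars pregnant patients. Inclusion criterion 8 says that, on re-enrolment, only screening procedures that have fallen outside their window are repeated.

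**Risk.** Section 8.2.1.9 describes embryo deaths and great-vessel and skull malformations in rats given cobimetinib at about 0.9 to 1.4 times human exposure. It advises against use in pregnancy and makes contraception mandatory.

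**The concern.** Exclusion 17 is enforced before dosing by a single scheduled test. That test does its job only if conception is unlikely between the test and the first dose. The plan sets the two dates independently: the test may be as early as Day −28, while contraception need not begin until Day −15. A woman tested in the early part of the window can conceive afterwards, without breaking any rule, and be registered and dosed on a negative result that is still valid. Nothing then obliges the site to test her again for two full cycles.

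What is at stake is fetal exposure to a drug that the protocol itself treats as a potential teratogen. This is a participant-safety point. The sample size, the error rates and the 16-week progression-free endpoint are unaffected.

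**Working it through.** The plan gives no figure of its own for this interval, so there is none to reproduce. The check is calendar arithmetic, counting days back from the first dose.

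**Inputs**
- Earliest allowed pre-treatment test: 4 weeks = 28 days before the first dose (Study Calendar, note 1; note 13 does not shorten it).
- Required start of contraception: 15 days before the first dose (criterion 6 in the synopsis and 4.1; Appendix B).
- Cycle length: 28 days (section 7.4).
- Cobimetinib: Days 1 to 21 of each cycle (section 7.4.2).
- Registration: review of 1 to 2 days, then up to 14 days to the first dose, or 21 days under one sentence of 5.1.
- TP53 result, where status is not already known: on average 2 weeks after tissue is received (section 7.2).

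**Reading of the calendar.** The table is partly broken in the text available. The second pregnancy-test mark sits in the same column as amylase/lipase and tumor imaging. Imaging is described elsewhere as about every 8 weeks, which fits Day 1 of odd cycles. There is no mark at Cycle 1 Day 1 or Cycle 2 Day 1.

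**Gap between test and contraception.** 28 − 15 = 13 days, Day −28 to Day −16. A test on Day −15 or later leaves no gap.

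**Next scheduled test.** Cycle 3 Day 1 is 2 × 28 = 56 days after the first dose, study Day 57. The two scheduled tests can therefore be 28 + 56 = 84 days apart.

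**Age of a conception occurring in the gap**
- At the first dose: 16 to 28 days.
- At Cycle 3 Day 1: 16 + 56 = 72 to 28 + 56 = 84 days.

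**Scheduled cobimetinib doses before that test.** 2 × 21 = 42.

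**Can the plan's own timetable produce an early test?**
- Test on the day the eligibility documents are sent, first dose at the 2-week limit: 14 + 1 = 15 to 14 + 2 = 16 days old, so 0 to 1 day uncovered.
- The same under the 3-week sentence: 21 + 1 = 22 to 21 + 2 = 23 days old, so 7 to 8 days uncovered.
- Test when the tissue is received for TP53 typing: 14 days on average for the result plus up to 14 days to start = 28 days, before any review time. For these patients an early test can reach the limit of the window without a deviation.
- Re-enrolment adds no days, because the test still cannot be older than 28 days, but an in-window test need not be repeated.

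**The case against.** The strongest reply accepts the dates and disputes the weight.

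- **Thirteen days is the extreme.** It needs a test on exactly Day −28. With a test taken at document submission and the 2-week limit, the uncovered time is 0 to 1 day; the 7 to 8 day figure depends on one sentence in 5.1 that disagrees with the rest. This stands as a description of size. It does not remove the gap, and the TP53 waiting time makes earlier tests plausible.
- **There are other safeguards.** Exclusion 17 bars pregnancy itself, not just a positive test. Under the 2-week limit, registration falls at about Day −14 or later, when contraception is already due. A history and physical is done on Day 1 of each cycle, and investigators may order extra tests. These narrow the risk, but none of them requires a pregnancy test.
- **The exposed group is small.** The embryofetal evidence in the documents concerns cobimetinib only; no such finding is reported for idasanutlin. About 40% of patients are expected to be TP53-mutated (section 7.1), section 24.3.1 caps the arm at 33, and prior endocrine treatment makes postmenopausal patients likely. This is fair. The share of childbearing potential is not given, so the number cannot be stated in either direction.
- **A 7-day window is not shown to detect every case.** A conception on Day −16 would be 16 − 7 = 9 days old at a Day −7 test, and the documents give no detection lag. This also stands; the length of the window is for the sponsor to set.

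**Conclusion.** The point holds. As written, the plan lets exclusion 17 rest on a test that predates mandated contraception by up to 13 days, with no further scheduled test until study Day 57 and up to 42 scheduled cobimetinib doses in between. No other section requires a test nearer the first dose.

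The conclusion rests on reading note 1 as governing the pregnancy test, because no other note sets a window for it, and on the odd-cycle reading of the calendar. The figures are permitted limits. How often a test is taken before Day −15, and how many patients are of childbearing potential, cannot be taken from the documents. The change should be made because it is cheap and the possible harm is serious; it is not a threat to the trial's efficacy conclusions.

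**What to change.** Amend note 13 of the Study Calendar to require a negative pregnancy test shortly before Cycle 1 Day 1, expressly overriding the 4-week window of note 1. With 7 days as an example, the earliest allowed test falls 15 − 7 = 8 days after contraception starts. The sponsor should choose the number of days with the detection lag of its assay in mind. The Cycle 3 Day 1 test and later ones can stay as they are.

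An alternative is to require contraception from the date of the pre-treatment test. That closes the gap without another test, but leaves a result up to 28 days old as the only check before dosing.

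**Cost.** The 7-day example means one repeat test, with the result in hand before dosing, for women tested on Day −28 to Day −8: 28 − 7 = 21 of the 28 days now allowed. Either route is a protocol amendment needing IRB approval at each institution (section 22.2).

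The same amendment could tidy two clerical points. Criterion 6 and Appendix B differ on childbearing potential, notably on tubal ligation, and note 13 depends on that term. Criterion 6 and section 8.2.1.9 also point to Appendix C for contraception, which is in Appendix B.

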### **Exclusion Criteria**

- 1. Prior therapy with anti-PD-L1 and anti-PD1 antibodies, MEK inhibitors or MDM2 antagonists.
- 2. No more than 3 lines of chemotherapy in the metastatic setting
- 3. No concurrent anticancer therapy. Required washout from prior therapy:
  - Endocrine therapy: no required wash-out
  - Chemotherapy: 14 days
  - Major surgery: 14 days (provided wound healing is adequate)
  - Radiation: 7 days
  - Investigational/Biologic Therapy (half –life ≤ 40 hours): 14 days
  - Investigational/Biologic Therapy (half –life > 40 hours): 28 days
  - Use of corticosteroids or immunosuppressive medication is exclusionary, except the following in the absence of active autoimmune disease:
    - o Subjects are permitted the use of corticosteroids with minimal systemic absorption (e.g. topical, ocular, intra-articular, intranasal, and inhaled);
    - Systemic corticosteroids at physiologic doses ≤10 mg/day of prednisone or equivalent are permitted;
    - Adrenal replacement steroid doses including doses > 10 mg daily prednisone are permitted;
    - o A brief (less than 3 weeks) course of corticosteroids for prophylaxis (e.g. CT scan premedication against contrast dye allergy) or for treatment of non-autoimmune conditions (e.g. delayed-type hypersensitivity reaction caused by a contact allergen) is permitted.
- 4. Previous malignant disease other than breast cancer within the last 5 years, with the exception of basal or squamous cell carcinoma of the skin,

cervical carcinoma in situ, or low-risk cancers considered curatively treated (i.e. complete remission achieved at least 2 years prior to first dose of study drugs AND additional therapy not required while receiving study treatment).

- 5. All subjects with brain metastases, except those meeting the following
  - Brain metastases that have been treated locally and are clinically stable for at least 2 weeks prior to enrollment
  - No history of intracranial or spinal cord hemorrhage
  - No evidence of interim CNS disease progression
  - Metastasis to the midbrain, pons, and medulla
  - No ongoing neurological symptoms that are related to the brain localization of the disease (sequelae that are a consequence of the treatment of the brain metastases are acceptable.
  - Subjects must be either off steroids or on a stable or decreasing dose of ≤ 10 mg daily prednisone (or equivalent)
- 6. Receipt of any organ transplantation including allogeneic stem-cell transplantation.
- 7. Significant acute or chronic infections including, among others:
  - Known history of testing positive for human immunodeficiency virus (HIV), or acquired immunodeficiency syndrome (AIDS).
  - Active tuberculosis
  - Positive test for hepatitis B virus (HBV) surface antigen (and/or core antibody) and/or confirmatory hepatitis C virus (HCV) RNA (if anti-HCV antibody tested positive).
- 8. Interstitial lung disease that is symptomatic or which may interfere with the detection or management of suspected drug-related pulmonary toxicity.
- 9. Active autoimmune disease with reasonable possibility of clinically significant deterioration when receiving an immunostimulatory agent:
  - Subjects with Type 1 diabetes mellitus, vitiligo, psoriasis, hypo- or hyperthyroid disease not requiring immunossupressive treatment are eligible
  - Subjects requiring hormone replacement with corticosteroids are eligible if the steroids are administered only for the purpose of hormonal replacement and at doses ≤ 10 mg or 10 mg equivalent prednisone per day
  - Administration of steroids through a route known to result in a minimal systemic exposure (topical, intranasal, intra-ocular, or inhalation) are acceptable.
- 10. Uncontrolled asthma [defined as having 3 or more of the following features of partially controlled asthma within 28 days prior to starting study treatment: Daytime symptoms more than twice per week, any limitation of activities, any nocturnal symptoms/awaking, need for reliever/rescue inhaler more than twice per week, or known lung function (PEF or FEV1) without administration of a bronchodilator that is < 80% predicted or personal best (if known)].
- 11. Current symptomatic congestive heart failure (New York Heart

Association > class II), unstable cardiac arrhythmia requiring therapy (e.g. medication or pacemaker), unstable angina (e.g. new, worsening or persistent chest discomfort), or uncontrolled hypertension (systolic > 160 mmHg or diastolic > 100mmHg). Or any of the following occurring within 6 months (180 days) prior to first dose of study drugs: Myocardial infarction, coronary/peripheral artery bypass graft, cerebrovascular accident or transient ischemic attack. (Use of antihypertensive medication to control blood pressure is allowed.)

- 12. Concurrent treatment with a non-permitted drug as well as foods or supplements that are strong or moderate CYP3A4 enzyme inducers or inhibitors. Any of the above has to be discontinued at least 7 days prior to Cycle 1/ Day 1 of study treatment. See supplemental packet for quidance.
- 13. Requirement of anticoagulant therapy with oral vitamin K antagonists such as Coumadin (warfarin). Low-dose anticoagulants for the maintenance of patency in a central venous access device or the prevention of deep vein thrombosis or pulmonary embolism is allowed. Therapeutic use of low molecular weight heparin is allowed provided patients are safely able to interrupt it prior to biopsy procedures.
- 14. Persisting non-hematological toxicity related to prior therapy that has not reduced to Grade 1 [National Cancer Institute Common Toxicity Criteria for Adverse Events (NCI CTCAE) version 5.0]; however, alopecia and sensory neuropathy Grade ≤ 2 are acceptable and Grade ≤ 2 nonhematological toxicities well controlled with medical management are allowed (for example: hypomagnesemia well controlled on magnesium replacement).
- 15. Known severe (Grade ≥ 3 NCI-CTCAE) hypersensitivity reactions to monoclonal antibodies, or history of anaphylaxis.
- 16. Vaccination within 28 days of the first dose of study drugs and while on trial is prohibited, except for administration of inactivated vaccines (for example, inactivated influenza vaccine).
- 17. Pregnant or breastfeeding females.
- 18. Known current alcohol or drug abuse
- 19. Prisoners or subjects who are involuntarily incarcerated.
- 20. Known psychiatric condition, social circumstance, or other medical condition reasonably judged by the patient's study physician to unacceptably increase the risk of study participation; or to prohibit the understanding or rendering of informed consent or anticipated compliance with scheduled visits, treatment schedule, laboratory tests and other study requirements.
- 21. Known risk factors for ocular toxicity (cobi arm only), consisting of any of the following:
  - presence of serous retinopathy within 6 months of protocol enrollment
  - presence of retinal vein occlusion (RVO) within 6 months of protocol enrollment

